### **1.3.2 Potential Benefits**

There is no direct benefit to the subject. Results from this study may help to determine the effects of ozone on the human airways and cardiovascular system.

## **2 OBJECTIVES**

### **2.1 Study Outcome Measures**

#### **2.1.1 Primary**

The primary endpoint is the change in nasal PMN counts, measured in nasal lavage fluid, between FA and O3.

#### **2.1.2 Secondary**

Secondary endpoints to be measured include NEC and ELF for inflammatory endpoints, spirometry for change from baseline, change in cardiovascular endpoints FMD, HRV and LV ultrasound in FA vs O3.

Exploratory endpoints correlation of ambient ozone level using a novel, wearable device.

### **3 STUDY DESIGN**

This is a double blind, randomized, crossover study of healthy individuals, who are exposed to relevant levels of ozone vs filtered air, for 6.5 hours and while at rest. This is intended to mimic exposure to ozone levels of typical summer day, on a typical sedentary day.

Multiple samples will be collected, for both nasal and cardiovascular endpoints. Additional information will be collected in for phenotype comparisons.

#### **3.1 Subject Inclusion Criteria**

In order to be eligible to participate in this study, an individual must meet all of the following criteria:

- Provide signed and dated informed consent form.
- Willing to comply with all study procedures and be available for the duration of the study.
- Aged 18 to 50.
- In good general health as evidenced by medical history with Vital signs within normal limits on admission to the study: SpO2  $\geq$  94%, systolic blood pressure between 150-90 mm Hg, diastolic blood pressure between 100-60 mm Hg, afebrile.
- FEV1 of at least 80% of predicted.

#### **3.2 Subject Exclusion Criteria**

An individual who meets any of the following criteria will be excluded from participation in this study:

- Medical condition, laboratory finding, or physical exam finding including any chronic medical condition considered by the PI as a contraindication to the exposure study, including significant cardiovascular disease, diabetes requiring medication, chronic renal disease, chronic thyroid disease, or kidney disease, which precludes participation.
- Use of disallowed concomitant medications including systemic or inhaled steroids, NSAIDS or aspirin within 72 hours of dosing, and inability to withhold these medications prior to each session of the study.
- Pregnancy or nursing.

- History of current tobacco use, or more than a lifetime 5 pack year history of tobacco use.

### **3.3 Strategies for Recruitment and Retention**

Subjects will complete either UNC CEMALB screening and database protocol #98-0799 or the Recruitment and Screening of Potential Participants for EPA studies #95-0518 prior to enrollment into this study.

### **3.4 Treatment Assignment Procedures**

A randomization table will be provided by [name], who provides statistical assistance to the CEMALB. TRC maintains the blinding list, and will release it to the study team at the end of the study, or earlier if an interim analysis is done.

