## PROTOCOL SUMMARY

Title:	Human biological responses to low level ozone
Précis:	Subjects will be exposed to low levels of ozone approximating a typical, metropolitan, summer day, ranging from 0.06ppm to 0.08ppm. Subjects will be sedentary, to approximate a typical day. Nasal, pulmonary and cardiovascular endpoints will be measured.
Objectives:	Primary: To explore whether low level ozone exposure, reflective of a typical metropolitan summer day, will cause measurable inflammation in nasal cells or affect cardiovascular endpoints in a sedentary human.
Population:	15 healthy control subjects
Description of Intervention:	Subjects will be exposed to low level ozone, ranging from 0.06ppm to 0.08ppm during the course of the exposure session. Subjects will be sedentary. Nasal, pulmonary and cardiovascular endpoints will be measured.
Study Duration:	60 months.
Subject Participation Duration:	No more than 7 weeks.
Estimated Time to Complete Enrollment:	24 months.

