### **3.6 Study Product Description**

Ozone is generated by TRC, a contractor for the US EPA. They have procedures in place both for generating and monitoring the O3 concentrations, and they will provide a separate protocol operations plan for this study.

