### **3.7 Accountability Procedures for the Study Product**

At the completion of the study TRC will provide a written report for all chamber exposures. The study may be unblinded at the request of the PI or other study medical doctor in the event a subject has an unexpected event and unblinding is necessary for subject treatment or for study continuation.

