10. Perform nasal epithelial cell biopsy for baseline: a non-invasive biopsy procedure will be performed to retrieve a small cluster of cells from each of the nasal cavities. For the biopsy procedure, the subject will be seated comfortably in a straight-backed chair or reclining on an exam table with the head tilted as far back as possible while remaining comfortable. A short, sterile plastic sampling device called a curette will be inserted into one of the nasal cavities and the surface of the nasal cavity will be stroked several times for approximately 5 seconds in order to obtain a small cluster of cells. Only one side will be collected at this visit. The investigator, study physicians or other trained staff will collect these samples.
11. Introduce the subject to the chamber area by walking them through.
12. Subjects will be discharged with contact information for a study physician on call.

13. **Psychological surveys:** Once subjects have been qualified, they will be emailed a link to complete psychological surveys. These will be performed at home, and at the convenience of the subject, prior to the first exposure session.

Once the subject is deemed eligible, they will return for a baseline day to collect pre-exposure measurements. This visit must occur no less than 3 days and no more than 6 weeks after the screening visit. Subjects will be asked to withhold NSAIDs and antioxidant vitamins for 7 days prior, and to arrive fasting (water is acceptable). We will update any changes in medical history, including medication use, collect vital signs, and perform spirometry.

The following samples will be collected:

1. **Urine pregnancy test:** For all women, if more than 7 days have passed since the prior test.
2. **Epithelial lining fluid (ELF) collection.** This is done by having the subject spray normal saline into the nose, and then insert a small filter paper into each nostril. Nose clips are applied for 2 minutes, then the filter paper is removed. These samples are collected by study staff.
3. **Nasal lavage (NL):** This is done by repetitive spraying of sterile normal saline irrigation solution into the nostril, followed by voluntary expelling of the fluid by the subject into a specimen collection cup. Both nostrils are sampled, these samples will be collected by study staff,

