7. The subject will enter the chamber. The atmosphere will be determined randomly and will be either filtered clean air or ozone. The ozone concentration will be varied from 0.06 to 0.08 through the course of the exposure, and the exposure will last for 6.5 hours. The subjects will rest during the exposure with intermittent mild walking on the treadmill. Subjects will be provided with a low fat lunch to eat while they are in the chamber. HR will be monitored continually while the subject is in the chamber, and blood pressure will be measured hourly. A symptom questionnaire will be completed at the end of the exposure period. Immediately upon exiting the chamber, the subjects will undergo HRV for up to 30 minutes, followed by FMD and LV strain measurement. ELF and NL samples will be collected. Nasal epithelial cells (NEC) will be obtained from the opposing nostril from screening or exposure session 1.

Spirometry will be obtained prior to discharge, and at any point during the study if the subject experiences any distress or shortness of breath. Subjects will be discharged with contact information for a study physician on call.

Subjects will return 24 hours later. After updating the health history and collecting vital signs, the following measurements/samples will be collected:

1. Symptom questionnaire
2. HRV for up to 30 minutes
3. Venipuncture as collected at screening day

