4. ELF
5. NL
6. Spirometry
7. Sputum induction

The subjects will be discharged with contact information for a study physician. They will be scheduled to return for a second session, with a minimum of 2 weeks and a

maximum of 6 weeks between exposures. The sessions will be identical except for the atmosphere in the chamber, which is randomized.

Baseline measurements provide safety information prior to each exposure. Given the level of the O3 and the procedures that subjects are asked to undergo, we do not anticipate any health concerns, but if they do arise, they will be immediate, therefore there are no scheduled visits beyond day 3 of the 2nd session. However, subjects will be encouraged to contact the study coordinator or physician at any time up to a month later if they have any concerns regarding their health or effects from the study.

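### If an interim analysis is done, section 3.4 sends the blinding list to an undefined study team, with no limit on recipient or on which subjects' codes are released

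*Combined protocol and SAP*

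**What the plan says.** Section 3.4 gives TRC custody of the blinding list and says that TRC "will release it to the study team at the end of the study, or earlier if an interim analysis is done". This is the only mention of an interim analysis in the document. Section 7 (Data Analysis) gives no timing, purpose, data cut-off or code recipient for one.

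Section 3 describes the design: "This is a double blind, randomized, crossover study of healthy individuals". Section 7 also calls the study double blind. On the two exposure sessions, section 4 says: "The sessions will be identical except for the atmosphere in the chamber, which is randomized". The planned size in the Protocol Summary is "15 healthy control subjects".

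The only other unblinding provision is in section 3.7: "The study may be unblinded at the request of the PI or other study medical doctor". It applies when a subject has an unexpected event and is not an interim-analysis rule. Section 7 ends by placing the statistical analyses under the supervision of the Biostatistics Core director, but does not say that this person is the one who receives the codes.

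**The concern.** A double blind in a crossover has to hold until a subject's second session has been measured. Section 3.4 contains a written rule that, if used, hands over the list before then. The rule names the study team as recipient and covers the whole list. Because the two sessions differ only in atmosphere, one code reveals both of a subject's sessions. The full list would also show the sequence of subjects not yet exposed.

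At stake is the credibility of measures that depend on coaching, effort or operator technique, chiefly spirometry and FMD, which are secondary endpoints. Some decisions also stay open while sessions remain. The investigator may end a subject's participation (section 3.5), and a study doctor decides whether a subject with a new medication may proceed (section 3.9). Blinding normally protects these too.

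**Working it through.** **1. Is the early release restricted anywhere?**

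- Section 3.4: the recipient is the study team, and the list is not qualified by subject or session.
- Section 3.7: release for a medical event only.
- Section 7: analyses are supervised from the Biostatistics Core, but no sole recipient and no separation from assessors is stated.
- Section 3.6: of TRC, the protocol says "they will provide a separate protocol operations plan for this study". That plan is introduced alongside generating and monitoring ozone. The protocol does not say that it governs code release, and it was not available to check.

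Within this document, the answer is no.

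**2. Do the people who would receive codes also take measurements?**

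For the screening nasal biopsy, section 4 says: "The investigator, study physicians or other trained staff will collect these samples". It has study staff collect lining fluid and lavage at baseline. For the exposure day it says: "Immediately upon exiting the chamber, the subjects will undergo HRV for up to 30 minutes, followed by FMD and LV strain measurement". No operator is named there, nor for that day's spirometry and nasal sampling. Overlap is a reasonable inference, but it is not documented.

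**3. How many sessions could remain?**

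With 15 subjects and two sessions each there are 30 sessions. If *k* subjects have finished at the look, at most 2 × (15 − *k*) remain:

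- *k* = 5: 2 × 10 = 20
- *k* = 8: 2 × 7 = 14
- *k* = 14: 2 × 1 = 2

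**4. What could that do to a final test?**

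The plan gives no figure for this, so what follows is an illustration. The test is the two-sided paired t test at 0.05 that section 7 uses for sample size. As a check on that reading, take the SDs of 31 and 17 at correlation 0. The SD of the difference is √(31² + 17²) = 35.36. With an effect of 36, the smallest N reaching 90% power is 13, as the plan states. The point does not depend on that figure.

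Assumptions, none taken from the documents:

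- There is no true ozone effect, and within-subject differences have SD 1.
- Knowing the code adds *b* SD to the difference in each of the 15 − *k* unfinished subjects, all in the same direction. This is an upper case for anyone who had already done session 1 at the look.

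The average shift over all 15 subjects is *b* × (15 − *k*)/15. The test is t = mean/(s/√15) on 14 degrees of freedom. False-positive rates come from 4,000,000 simulated trials:

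| Finished at look | *b* | Average shift | False-positive rate |
|---|---|---|---|
| any | 0 | 0 | 5.0% |
| 5 | 0.1 | 0.1 × 10/15 = 0.067 | 5.6% |
| 5 | 0.3 | 0.3 × 10/15 = 0.200 | 10.8% |
| 5 | 0.5 | 0.5 × 10/15 = 0.333 | 21.0% |
| 8 | 0.1 | 0.1 × 7/15 = 0.047 | 5.3% |
| 8 | 0.3 | 0.3 × 7/15 = 0.140 | 7.7% |
| 8 | 0.5 | 0.5 × 7/15 = 0.233 | 12.2% |
| 14 | 0.1 to 0.5 | 0.007 to 0.033 | 5.0% |

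Section 7 also names a two-sample t test, a Mann-Whitney test and a random effects model, so these rates show scale only.

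**The case against.** The strongest reply is that the trigger is hypothetical. Section 7 plans no interim analysis for this small pilot, and if none is done the clause has no effect. That stands, and it is why the point is minor. It does not remove the point, because the protocol writes the rule that would govern a look and nothing else would limit it.

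The study team may also mean, or include, the statistician who would run the analysis. The term is undefined, so this cannot be excluded. A reader might infer that the people performing FMD, LV strain and spirometry will hold the codes. The document does not support that, since it names no exposure-day operators. The supportable defect is that the recipient is left open.

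The TRC operations plan might contain a restriction. The finding therefore holds for this document only.

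The size rests on an assumed shift. The 21% needs both an early look and 0.5 SD in all ten unfinished subjects. At 0.1 SD the rate barely moves, and after 14 finished subjects it does not move at all. This objection stands in full.

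Many measures have some protection. The primary endpoint is a laboratory count, HRV analysis is computer based, LV strain is quantified off-line by software, and spirometry follows ATS/ERS standards. What remains exposed is mainly acquisition and effort in a few secondary measures.

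**Conclusion.** The point holds as a conditional weakness in the release rule. Section 3.4 allows the blinding list to reach an undefined study team before the end of the study, without restricting the recipient or limiting release to completers. If a look is taken on those terms, the double blind claimed in sections 3 and 7 could end for staff who may still run sessions.

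Two stronger readings are not supported. A reader might infer that the trial will be unblinded midway, but no interim analysis is scheduled. A reader might also take the false-positive rates as an estimate of bias in this trial, or as applying to the primary endpoint. They are an illustration for an effort- or operator-dependent measure: about 5.6% to 21% after 5 finished subjects, 5.3% to 12% after 8, and 5.0% after 14, under an assumed 0.1 to 0.5 SD shift in every unfinished subject. Control of type I error for repeated testing is a separate matter and adds no weight here.

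This is a cheap improvement of minor severity.

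**What to change.** In section 3.4, keep release to the study team at the end of the study, and replace the clause on earlier release with:

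> For any interim analysis, TRC releases codes only to a Biostatistics Core statistician who does not collect or read samples, and only for subjects who have completed both sessions; while sessions remain, the study team sees no individual codes and no results by exposure.

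Leave the medical unblinding in section 3.7 unchanged.

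The cost is one sentence, with no added subjects, visits or procedures, and the Biostatistics Core already supervises the analyses. The downside is that the study team does not see unblinded interim data. The completer limit also leaves out subjects between sessions, but a paired comparison could not use them in any case.

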### **3.5 Subject Withdrawal**

Subjects may withdraw voluntarily from the study at any time. The investigator may terminate a subject's participation if there is any concern for the health or well-being of the subject, or if the subject fails to follow the study requirements.

### **3.6 Study Product Description**

Ozone is generated by TRC, a contractor for the US EPA. They have procedures in place both for generating and monitoring the O3 concentrations, and they will provide a separate protocol operations plan for this study.

### **3.7 Accountability Procedures for the Study Product**

At the completion of the study TRC will provide a written report for all chamber exposures. The study may be unblinded at the request of the PI or other study medical doctor in the event a subject has an unexpected event and unblinding is necessary for subject treatment or for study continuation.

### **3.8 Assessment of Subject Compliance with Study Product Administration**

Subjects will be queried regarding adherence to medication restrictions.

### **3.9 Concomitant Medications/Treatments**

Subjects will be queried regarding concomitant medication use at each visit. Any new medications will be documented and the PI or covering medical doctor will be notified, and that individual will decide if the subject may proceed with the study.

---

## 4 STUDY SCHEDULE

Subjects will arrive for a consent visit and screening for the study. After informed consent is obtained, we will:

1. Collect/update medical history, including any medications
2. Collect vital signs, including pulse, RR, BP, temp, SpO2 and breath sounds.
3. Measure height and weight.
4. Pregnancy test will be done for all women
5. Obtain standard 12-lead ECG for baseline measurement.
6. Perform spirometry according to ATS/ERS recommendations.
7. Perform venipuncture for 50ml of blood for clinical labs, including CBC Diff, chemistries as well as baseline research labs.
8. Perform physical examination (by a study doctor) to evaluate the subject for eligibility.
9. Collect sputum for baseline measurements. Induced sputum is a method for obtaining lower airway secretions. Subjects will be asked not to eat for 2 hours prior to this test as food residue in the mouth may contaminate the samples. Any subject who comes to this study with a diagnosis of mild asthma will be pre-treated with 2-4 puffs of albuterol prior to sputum induction. Subjects will breathe saline from an ultrasonic nebulizer through a mouthpiece for 7 minutes of each saline concentration (3%, 4%, and 5%) while seated. After the first inhalation period subjects will be asked to rinse their mouths out with water, spit into the sink, and then gargle. Then they will clear the throat, and blow their nose. Subjects are then encouraged to expectorate samples from deep in the chest and spit them into a separate sample cup. Spirometry will be assessed after each saline level to ensure no lung function decrements. If the FEV1 decreases 10% or more from baseline, the subject will not be advanced to the next level of saline; however the same level may be repeated once. If the FEV1 drops 20% or more the procedure is stopped and, if necessary, 2 puffs of albuterol will be given. The physician may prescribe a second albuterol MDI treatment at his/her discretion.
10. Perform nasal epithelial cell biopsy for baseline: a non-invasive biopsy procedure will be performed to retrieve a small cluster of cells from each of the nasal cavities. For the biopsy procedure, the subject will be seated comfortably in a straight-backed chair or reclining on an exam table with the head tilted as far back as possible while remaining comfortable. A short, sterile plastic sampling device called a curette will be inserted into one of the nasal cavities and the surface of the nasal cavity will be stroked several times for approximately 5 seconds in order to obtain a small cluster of cells. Only one side will be collected at this visit. The investigator, study physicians or other trained staff will collect these samples.
11. Introduce the subject to the chamber area by walking them through.
12. Subjects will be discharged with contact information for a study physician on call.

13. **Psychological surveys:** Once subjects have been qualified, they will be emailed a link to complete psychological surveys. These will be performed at home, and at the convenience of the subject, prior to the first exposure session.

Once the subject is deemed eligible, they will return for a baseline day to collect pre-exposure measurements. This visit must occur no less than 3 days and no more than 6 weeks after the screening visit. Subjects will be asked to withhold NSAIDs and antioxidant vitamins for 7 days prior, and to arrive fasting (water is acceptable). We will update any changes in medical history, including medication use, collect vital signs, and perform spirometry.

The following samples will be collected:

1. **Urine pregnancy test:** For all women, if more than 7 days have passed since the prior test.
2. **Epithelial lining fluid (ELF) collection.** This is done by having the subject spray normal saline into the nose, and then insert a small filter paper into each nostril. Nose clips are applied for 2 minutes, then the filter paper is removed. These samples are collected by study staff.
3. **Nasal lavage (NL):** This is done by repetitive spraying of sterile normal saline irrigation solution into the nostril, followed by voluntary expelling of the fluid by the subject into a specimen collection cup. Both nostrils are sampled, these samples will be collected by study staff,
4. **Spirometry:** Standard spirometry to obtain FEV1 and FVC measurements will be done prior to sputum induction. This is done by having the subject exhale forcefully and completely into a mouth piece attached to a pneumotach. This will be repeated several times, and the procedure will be done following ATS/ERS standards.
5. **Flow-mediated brachial artery dilation (FMD):** This measurement is made by imaging the brachial artery with an ultrasound device. The blood flow to the artery is occluded for 5 minutes, and the artery is again imaged when blood flow is resumed.
6. **Left ventricular strain:** Left ventricular contractility will be assessed by measuring global longitudinal strain using 2-dimensional speckle tracking echocardiography. Apical 4-chamber, 2-chamber, and long axis 2-dimensional ultrasound images of the heart will be acquired using a Philips EPIQ 7 ultrasound machine and stored for subsequent off-line analysis. Global longitudinal strain will be quantified using Philips QLAB advanced quantification software.

The subject will be discharged to home with contact information for a study physician who is on-call if the subject has any health concerns. The subject will return the next morning, and after health history is updated and vital signs collected, the following will take place:

1. **Heart rate variability (HRV):** Standard ECG leads will be placed on the subject's chest, and connected to a monitor that records the heart rate and rhythm. The subject will be asked to lie supine in a quiet, darkened room for up to 30 minutes. The subject will do this before the exposure and immediately after the exposure. The analysis for this measurement is computer based.
2. **Spirometry:** Standard spirometry will be measured prior to the subject entering the exposure chamber.
3. **Ozone monitor:** Subjects will wear an experimental ozone monitor, which is on a bracelet. This is to validate the wearable monitor in an environment with known ozone concentration.
4. **Telemetry:** Standard 3 lead ECG monitoring will be done while the subject is in the exposure chamber.
5. **Symptom questionnaire:** Subjects will be asked to complete a symptom questionnaire prior to entering the chamber.
  
7. The subject will enter the chamber. The atmosphere will be determined randomly and will be either filtered clean air or ozone. The ozone concentration will be varied from 0.06 to 0.08 through the course of the exposure, and the exposure will last for 6.5 hours. The subjects will rest during the exposure with intermittent mild walking on the treadmill. Subjects will be provided with a low fat lunch to eat while they are in the chamber. HR will be monitored continually while the subject is in the chamber, and blood pressure will be measured hourly. A symptom questionnaire will be completed at the end of the exposure period. Immediately upon exiting the chamber, the subjects will undergo HRV for up to 30 minutes, followed by FMD and LV strain measurement. ELF and NL samples will be collected. Nasal epithelial cells (NEC) will be obtained from the opposing nostril from screening or exposure session 1.

Spirometry will be obtained prior to discharge, and at any point during the study if the subject experiences any distress or shortness of breath. Subjects will be discharged with contact information for a study physician on call.

Subjects will return 24 hours later. After updating the health history and collecting vital signs, the following measurements/samples will be collected:

1. Symptom questionnaire
2. HRV for up to 30 minutes
3. Venipuncture as collected at screening day

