**Exposure visit:**  
Vital signs will be collected, and subject will be queried for AEs. HRV will be obtained, spirometry performed, O3 monitor placed, telemetry placed, and symptom questionnaire obtained. A 6.5 hour exposure at O3 levels varying from 0.06 to 0.08 with the subject resting or with mild treadmill walking will take place. At the end of exposure the following samples will be collected: Symptom questionnaire, HRV, FMD, LV ultrasound, ELF and NL, spirometry.

Visit 4  
24 hours later

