## 7 DATA ANALYSIS

Aim 1. Characterize ozone induced changes in nasal PMN counts.

This is a randomized, double blind, crossover pilot study, studying the changes in cells of nasal lavage (neutrophilla) after low-level ozone exposure. First, descriptive analysis will be conducted to examine potential ozone exposure effect and period effect. Second, two sample tests such as t-test and Mann Whitney test will be used to compare changes in response in clean air and ozone exposure groups. In general, carry-over effect is first tested. In the absence of significant carry-over effect, pooled data from both periods can be used to estimate the ozone exposure effect. Otherwise, only period 1 data can be used. We will report effect estimates, standard deviation as well as confidence intervals for ozone exposure effect and potential period effect. Finally, a random effects model will be fitted to assess the ozone exposure effect. Confidence intervals will be reported.

Aim 2. Characterize ozone induced changes in inflammatory cytokines in nasal epithelial cell (NEC) biopsy and nasal epithelial lining fluid ELF

The analysis plan is the same as in Aim 1.

Aim 3. Characterize ozone induced changes in FMD, HRV, LVS, Brachial artery ultrasound, ambulatory ECG measures, & other cardiovascular measures.

The analysis plan is the same as in Aim 1.

Aim 4. Characterize ozone induced changes in spirometric measures

The analysis plan is the same as in Aim 1.

Aim 5. Investigate the performance of a wearable monitor for ambient ozone measurement.

There are 2 current devices which will be used (descriptions and photos attached. The subject may wear one or both of these devices. The purpose of these devices at this time is strictly to assess the measured values obtained by the devices compared to the known O3 atmosphere. However, as these devices are prototypes there are two important questions. The

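### NEC has one pre-exposure sample, from one nostril at screening, and nostril and scrape history run with period, yet Aim 2 takes over the Aim 1 analysis of changes unadapted

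*Combined protocol and SAP*

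**What the plan says.** **Sampling.** Item 10 of the screening list in Section 4 reads "Perform nasal epithelial cell biopsy for baseline", and adds "Only one side will be collected at this visit". The same item also describes the procedure as one to "retrieve a small cluster of cells from each of the nasal cavities", which does not agree with sampling one side.

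Once eligible, subjects attend a visit for which "they will return for a baseline day to collect pre-exposure measurements". Its list has ELF, nasal lavage, spirometry, FMD and left ventricular strain, but no NEC. The pre-chamber list and the 24-hour list have no NEC either. After exposure, Section 4 states: "Nasal epithelial cells (NEC) will be obtained from the opposing nostril from screening or exposure session 1". Of the second session it says: "The sessions will be identical except for the atmosphere in the chamber, which is randomized".

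The exposure-visit box of the schematic leaves NEC out: "At the end of exposure the following samples will be collected: Symptom questionnaire, HRV, FMD, LV ultrasound, ELF and NL, spirometry".

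**Analysis.** Section 2.1.2 names NEC as a secondary endpoint. For Aim 2, Section 7 says only: "The analysis plan is the same as in Aim 1". Aim 1 has four relevant parts:
- a descriptive look at exposure and period effects;
- two-sample tests (t or Mann-Whitney) of changes in response;
- a carry-over test, with a fallback to period 1 alone if it is significant;
- a random effects model whose terms are not listed.

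**The concern.** The Aim 1 analysis suits lavage and ELF, which have a baseline in each session. NEC has no session baseline, and its two post-exposure samples do not come from equivalent sites. The plan does not say what an NEC change is measured from, or how side and earlier scraping are handled.

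Three things are at stake for this endpoint. A change from screening would mean one thing in period 1 and another in period 2. Any systematic nostril or re-scraping difference would enter the error term if period is left out. And the period effect that Section 7 promises to report would mix time, side and scrape history.

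**Working it through.** **The plan's own figures.** The documents give no figure for NEC. The sample-size table concerns nasal PMN. With SD of the difference = sqrt(31² + 17² − 2ρ·31·17) = 35.36, 30.56 and 26.89 at ρ = 0, 0.3 and 0.5, an effect of 36 and a two-sided paired t test, all six N reproduce (10, 13, 8, 10, 7, 9). That table is not in question here.

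**Nostril trace.** Call the screening nostril A.

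| Sample | Nostril | Scraped earlier in the study? | Change from screening |
|---|---|---|---|
| Screening | A | no | – |
| Session 1, post-exposure | B | no | B − A, between nostrils |
| Session 2, post-exposure | A | yes, at screening | A − A, same nostril, re-scraped |

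The *or* in the Section 4 sentence is loose. If session 2 were meant to be opposite to screening, both changes would be between nostrils, and session 2 would re-scrape the nostril used in session 1. Scrape history would still follow period.

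**Age of the screening sample (Section 4 windows).** The baseline day is 3 to 42 days after screening, and exposure is the next morning, so 4 to 43 days. The second exposure is 14 to 42 days later: 4 + 14 = 18 to 43 + 42 = 85 days. The Protocol Summary limits participation to 7 weeks (49 days). Counted from screening, with the follow-up visit one day after exposure, the second exposure could be no later than about day 48. The two statements conflict at the upper end.

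**What the single baseline does within subject.** With screening value S and post-exposure values Y1 and Y2, (Y2 − S) − (Y1 − S) = Y2 − Y1. It cancels.

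**What it does in a period-1-only comparison.** Assume equal variances and a screening-to-exposure correlation ρ, which the documents do not give. Var(Y − S) = 2σ²(1 − ρ) against Var(Y) = σ², so the SE is multiplied by sqrt(2(1 − ρ)):

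| ρ (assumed) | 0 | 0.3 | 0.5 | 0.7 |
|---|---|---|---|---|
| SE factor | 1.41 | 1.18 | 1.00 | 0.77 |

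**What a two-sample test on data from both periods does.** Take σ = 1 and the same ρ between all three samples. The two-sample variance of changes is 4(1 − ρ)/n, and the paired variance is 2(1 − ρ)/n, so the SE ratio is 1.41 at every ρ. With no baseline subtracted, the two-sample variance is 2/n and the SE ratio is 1/sqrt(1 − ρ): 1.00, 1.41 and 1.83 at ρ = 0, 0.5 and 0.7. The loss thus comes from ignoring the pairing.

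**What omitting period does.** Let g be an additive nostril/re-scrape shift in session 2. The unadjusted mean of ozone minus air carries a bias of g(n1 − n2)/(n1 + n2), where n1 subjects receive ozone second. At 8:7 this is g/15 = 0.067g. With an assumed 8:5 split of completers it is 3g/13 = 0.23g.

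A simulation gives the cost in power. It used 4000 runs, n = 15 at 8:7, subject and residual SD both set to 1, and an assumed ozone effect of 1.2 residual SD.

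| g (residual SD) | 0 | 0.5 | 1 | 2 |
|---|---|---|---|---|
| Power, paired, no period term | 0.86 | 0.84 | 0.78 | 0.48 |
| Power, period-adjusted | 0.86 | 0.85 | 0.86 | 0.86 |

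The period-adjusted estimate showed no bias at any g.

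**The case against.** **Change may not mean change from screening.** Section 2.1.1 defines the primary change as between filtered air and ozone, and Section 2.1.2 attaches a baseline only to spirometry. On that reading the plan already intends post-ozone against post-air for NEC. This stands in part. A reader might infer that an invalid comparison is planned, but the documents leave the NEC change undefined. They do label the screening sample a baseline, and Aim 1 tests changes in response.

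**Period is not ignored.** Section 7 looks at period effects, reports them with intervals and fits a random effects model. Its carry-over-then-pool sequence resembles the standard two-stage crossover analysis, in which the two-sample test is applied to within-subject period differences and so removes both period and the shared baseline. This also stands in part: the text neither says that the tests are applied in that way nor puts period in the model.

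**The harm is limited.** Randomised sequence keeps ozone free of the nostril difference. In a period-1-only analysis both arms have the same nostril relation, so an additive shift cancels. No size for the shift is given, and the endpoint is secondary in a 15-subject pilot. All of this stands.

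**Conclusion.** The concern holds as a gap in the Aim 2 analysis. NEC has no session-specific baseline, and nostril and scrape history are aliased with period. The analysis carried over from Aim 1 defines neither the change nor a period term. The main cost is precision. Under the assumptions of the simulation, power without a period term falls from 0.86 to 0.78 at a shift of one residual SD and to 0.48 at two. The true shift is unknown and may be near zero.

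Four stronger readings are tempting and are not supported:
- That ozone is confounded with nostril. Sequence is randomised, and the bias is 1/15 of the shift at 8:7. The 3/13 figure needs a completer split that the documents do not give.
- That subtracting screening always adds noise. In period 1 it does so only when ρ is below 0.5; above that it helps.
- That the shared baseline causes the 1.41 SE ratio. That loss comes from an unpaired test, if one is used, and is not specific to NEC.
- That the baseline may be 85 days old. At least 18 days is firm under the Section 4 windows; the upper end conflicts with the 7-week limit.

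The primary endpoint and the sample size are unaffected.

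**What to change.** In Section 7, Aim 2, replace the cross-reference for NEC with its own statement:
- NEC is compared post-ozone against post-air within subject, with a period term. That term absorbs nostril and earlier scraping. The side sampled is recorded each time.
- NEC is not analysed as change from screening. The screening sample is descriptive, or a covariate if only period 1 is analysed.
- The NEC period effect is not interpreted as a pure time effect.

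In the protocol, reconcile:
- the schematic's exposure-visit list (no NEC) with Section 4, since the comparison needs a post-exposure NEC sample in both sessions;
- the two phrases on sides in the screening item, and the loose *or* in the post-exposure sentence;
- the Section 4 windows with the 7-week participation limit.

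The cost is one degree of freedom for period and some wording. No samples or subjects are added.
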